12.10.5. COVID-19 Experimental Agents

If any treatments for COVID-19 are planned for a study participant, please consult with the study medical monitor to ensure that relevant drug interactions are considered and to ensure that continued study participation remains appropriate.

12.10.6. COVID-19 Specific Data Capture

12.10.6.1. Capturing COVID-19 Specific Protocol Deviations

In order to summarise the impact of COVID-19 in a systematic way and in line with regulatory authorities' recommendations, any study-level impact around COVID-19 will be documented as a protocol deviation. This will include the permissible actions summarized in this Appendix, which are taken to protect patient safety, including the use of CAB + RPV or SOC ART as oral bridging as well as missed visits and assessments as a result of logistical challenges resulting from COVID-19.

Although the conduct of remote visits and the continuity of antiretroviral therapy, via oral bridging, are being utilized to protect patient safety, these events fall outside of the intent of the original protocol design, may have an impact on data interpretation, and thus will be characterized as protocol deviations for the purposes of data summary and analysis.

Any protocol deviations resulting from COVID-19 will be clearly identified as such within the protocol deviation description and summarised separately.

Please refer to your study procedure manual for specific details on capturing protocol deviations as a result of COVID-19.

12.10.6.2. Capturing COVID-19 Specific AEs and SAEs

It is important for the study team to describe COVID-19 related adverse events/serious adverse and their impact on study data and outcomes. Standardization of case definitions will facilitate future data analysis.

Please use the following guidance:

1. AEs should continue to be evaluated as to whether they meet SAE criteria as defined in the protocol, and if so, submitted according to established SAE reporting requirements. SAEs and AEs should be submitted following usual study procedures and timelines.

2. When an in-person clinic visit is not possible, please conduct a remote telehealth visit to assess for, and document any AEs/SAEs.
3. Investigators should use the WHO definition to classify COVID-19 cases. The definition below, released March 20, 2020, represents a time point for standardized collection. We recognize definitions are likely to continue to evolve. When reporting both serious and non-serious adverse events (related to COVID-19 infection, investigators should use the following Verbatim terms:
 - a) Suspected COVID-19 infection; or
 - b) Probable COVID-19 infection; or
 - c) Confirmed COVID-19 infection
4. Sites should contact the study Medical Monitor for questions related to definitions and reporting, and decisions around impact to study drug continuation.
5. A new COVID-19 infection Case Report Form will be added to the eCRF to collect additional details about the reported COVID-19 AE or SAE data. It is important to collect the correct information from each participant reporting a COVID-19 AE or SAE. Therefore, please use the CRF templates to help you collect this information, once available.

WHO Case Definition - March 20, 2020 Version ([https://www.who.int/publications-detail/global-surveillance-for-human-infection-with-novel-coronavirus-\(2019-ncov\)](https://www.who.int/publications-detail/global-surveillance-for-human-infection-with-novel-coronavirus-(2019-ncov))):

Suspected case:

- A. A patient with acute respiratory illness (fever and at least one sign/symptom of respiratory disease, e.g., cough, shortness of breath), AND a history of travel to or residence in a location reporting community transmission of COVID-19 disease during the 14 days prior to symptom onset;

OR

- B. A patient with any acute respiratory illness AND in contact (see definition of “contact” below) with a confirmed or probable COVID-19 case (see definition of contact) in the last 14 days prior to symptom onset;

OR

- C. A patient with severe acute respiratory illness (fever and at least one sign/symptom of respiratory disease, e.g., cough, shortness of breath; AND requiring hospitalization) AND in the absence of an alternative diagnosis that fully explains the clinical presentation.

Probable case:

- A. A suspect case for whom testing for the COVID-19 virus is inconclusive (Inconclusive being the result of the test reported by the laboratory).

OR

- B. A suspect case for whom testing could not be performed for any reason.

Confirmed case:

A person with laboratory confirmation of COVID-19 infection, irrespective of clinical signs and symptoms.

Covid-19 Contact:

A contact is a person who experienced any one of the following exposures during the 2 days before and the 14 days after the onset of symptoms of a probable or confirmed case:

1. Face-to-face contact with a probable or confirmed case within 1 meter and for more than 15 minutes;
2. Direct physical contact with a probable or confirmed case;
3. Direct care for a patient with probable or confirmed COVID-19 disease without using proper personal protective equipment; OR
4. Other situations as indicated by local risk assessments.

Note: for confirmed asymptomatic cases, the period of contact is measured as the 2 days before through the 14 days after the date on which the sample was taken which led to confirmation.

12.11. Appendix 11: Protocol Amendment History

The Protocol Amendment Summary of Changes Table for the current amendment is located directly before the Table of Contents (TOC).

Amendment 1, 22-Jun-2018

Overall Rationale for the Amendment: This amendment was completed to clarify procedures, adjust exclusion criteria, add missing risk assessment language and to clean up minor grammatical errors.

Section # and Name	Description of Change	Brief Rationale
Title page	Update of abbreviated study title	Updated to match eTrack
Section 1.1 Synopsis	Update of abbreviated study title	Updated to match title page
Section 1.3 Schedule of Activities	Clarification of procedures in SoA	Updated to provide clarity, removed completion of ISR diaries and match Time and Events tables in main protocol body.
Section 2.3.1 Risk Assessment	Addition of DTG + RPV risk assessment	Updated to add in most up to date safety and risk information
Section 5.2 Exclusion Criteria	Removal of Exclusion Criteria #7	Participants who are diagnosed with syphilis can enrol in study and be treated.
Section 8.1 Time and Events Table	Update of procedures	Updated to provide clarity and remove completion of ISR diaries.
Section 8.8 Pharmacokinetics	Addition of DTG PK storage sample information	Left out in error in original document
Section 11 References	Updated DTG IB reference to most up to date version	Update to ensure most up to date DTG safety and efficacy data is utilized.
Throughout	Minor editorial and document formatting revisions	Minor, therefore have not been summarized

#### **Description:**

- The purpose of this RAP is to describe the planned analyses and output to be included in the Clinical Study Report for Protocol 209035.
- This RAP is intended to describe the efficacy, safety and tolerability analyses required for the study.
- This RAP will be provided to the study team members to convey the content of the Statistical Analysis Complete (SAC) deliverable.

#### 1. INTRODUCTION

The purpose of this reporting and analysis plan (RAP) is to describe the analyses to be included in the Clinical Study Report for Protocol:

Revision Chronology:			
2018N356280_00	16-MAY-2018	Original	
2018N356280_01	22-JUN-2018	This amendment was completed to clarify procedures, adjust exclusion criteria, add missing risk assessment language and to clean up minor grammatical errors.	

#### 2. SUMMARY OF KEY PROTOCOL INFORMATION

## 2.1. Changes to the Protocol Defined Statistical Analysis Plan

The following are changes or deviations to the originally planned statistical analysis specified in the 209035 protocol amendment 1 [(Dated: 22/JUN/2018)]:

[figure not shown]
- PK samples would not be analysed and no PK outputs would be produced. Due to the
  vast amount of PK data available from other studies examining CAB LA + RPV LA
  PK data, CPMS decided not to evaluate PK data from this study. Additionally, the
  time points of PK sample collection correspond to peak, rather than trough,
  concentrations.
- Data from the digital assistance program was not collected due to cost concerns of using Ensemble and will not be analysed.

## 2.2. Study Objective(s) and Endpoint(s)

Objectives	Endpoints		
Primary Objectives	Primary Endpoints		
To demonstrate the antiviral activity of CAB LA + RPV LA every 2 months in suppressed HIV-1 infected antiretroviral therapy ART-experienced participants	
 
Proportion of participants with HIV-RNA ≥ 50 c/mL as per FDA Snapshot algorithm at Month 12
 
		
Secondary Objectives	Secondary Endpoints		
To demonstrate the antiviral and immunologic activity of CAB LA + RPV LA every 2 months and oral DTG +RPV once daily	
 
Proportion of participants with plasma HIV-1 RNA <50 c/mL (c/mL) at Month 12 using the FDA Snapshot algorithm
 
Proportion of participants with protocol-defined confirmed virologic failure (CVF) over time
 
Proportion of participants with HIV-RNA greater than or equal to 50 c/mL as per FDA Snapshot algorithm over time
 
Absolute values and changes from Baseline in viral load and CD4+ cell counts over time
 
		
To demonstrate the safety and	Incidence and severity of AEs and laboratory		

Objectives	Endpoints
tolerability of CAB LA + RPV LA every 2 months and oral DTG + RPV once daily  To assess viral resistance in participants experiencing protocol-	
 
abnormalities over time
 
Proportion of participants who discontinue treatment due to AEs over time
 
Change from Baseline in laboratory parameters over time
 
Incidence of treatment emergent genotypic and phenotypic resistance to CAB, RPV, and DTG + RPV
 

To assess participant reported health-related quality of life, treatment satisfaction, injection tolerability, and treatment acceptance.	
 
Change from Baseline (Day 1) in HIVDQoL at Months 6 and 12 (or Withdrawal)
 
Change from baseline (Day 1) in total "treatment satisfaction" score, and individual item scores of the HIV Treatment Satisfaction Status Questionnaire (HIVTSQs) at Months 6 and 12 (or Withdrawal)
 
Change in treatment satisfaction over time using the HIV Treatment Satisfaction Change Questionnaire HIVTSQc at Month 12 (or Withdrawal).
 

Exploratory Objectives	Exploratory Endpoints

 
To assess reason for switching using a single question
 
To assess preference using a single question
 
	
 
The 'Preference" question will be used to assess preference for CAB LA + RPV LA every 2 months compared to prior oral CAB + RPV regimen, at Month 12 using a single dichotomous preference question.
 
The "Reason for Switch" question will be administered at Day 1 (Baseline) to assess the reasons for willingness to switch to LA injectable ART or to another oral regimen.
 

#### 2.3. Study Design

- § All participants in LATTE administered oral CAB 30 mg + RPV 25 mg
- † Access commercially once Q8W is approved
- # Access longer term via commercial route. Participants will continue to receive DTG + RPV if located in a region where not commercially available.

# Design Features

The study is a Phase IIb, open-label, 2 arms, multicenter rollover study designed to assess the antiviral activity and safety of CAB LA + RPV LA administered every 2 months in approximately 100 adult HIV-1 infected participants from the LATTE study.

Participants who fulfill eligibility requirements will be entered into the study to receive CAB LA + RPV LA Q2M or the oral DTG + RPV regimen for at least 12 months, until commercially available.

Any participant who receives at least one dose of CAB LA and/or RPV LA and discontinues the CAB LA + RPV LA regimen for any reason will enter a 52-week LTFU Phase. Those participants must remain on suppressive HAART for at least 52 weeks after the last dose of CAB LA and/or RPV LA.

#### Dosing

#### Group 1:

First Injections (Loading Doses) – Day 1 and Month 2

#### Day 1:

- Receive last dose of oral CAB + RPV regimen
- Receive CAB LA 600 mg given as 1 X 3 mL IM injection
- Receive RPV LA 900 mg given as 1 X 3 mL IM injection

#### Month 2:

- Receive CAB LA 600 mg given as 1 X 3 mL IM injection
- Receive RPV LA 900 mg given as 1 X 3 mL IM injection

Maintenance Injections – every 2 months (Q2M) following Month 2 Month 4 to End of Study (two 3 mL injections every 2 months):

- Receive CAB LA 600 mg given as 1 X 3 mL IM injection
- Receive RPV LA 900 mg given as 1 X 3 mL IM injection

Overview of St	Overview of Study Design and Key Features			
	Group 2:			
	Day 1 to Month 12 (once daily FDC tablet taken with food):			
	Take one tablet of DTG 50 mg + RPV 25 mg once daily			
	See the protocol Table 2.			
Time &	Refer to Appendix 2: Schedule of Activities			
Events				
Treatment	Participants transitioning from the LATTE study on oral CAB + RPV treatment will			
Assignment	transition to their elected treatment regimen, either Q2M administration of CAB LA			
	+ RPV LA or oral DTG + RPV single tablet regimen.			
Interim	No Interim Analysis will be conducted.			
Analysis				

## 2.4. Statistical Hypotheses / Statistical Analyses

No statistical hypotheses of treatment comparisons will be conducted within this study.

#### 3. PLANNED ANALYSES

At least one analyses will be conducted to evaluate primary and secondary objectives of the protocol after all subjects have completed their visits at Month 12. Further data cuts and analyses may be conducted as necessary after Month 12 to support regulatory publications. The Month 12 analysis will be primary. Further analyses may be conducted when all subjects on CAB LA + RPV LA have completed their Month 26 visit or when all subjects have completed the study (final End-of-Study analysis).

## 3.1. Interim Analyses

No Interim Analysis will be conducted.

#### 3.2. Final Analyses

The primary analysis will be conducted to evaluate the primary objective of the study at Month 12. These analyses will be performed after the completion of the following sequential steps:

- 1. All participants have completed Month 12 as defined in the protocol.
- 2. All required database cleaning activities have been completed and final database release (DBR) and database freeze (DBF) has been declared by Data Management.

A final End-of-Study analysis will be conducted when all subjects have completed the study as defined in the protocol. Additional analysis may be conducted when all subjects on CAB LA + RPV LA have completed their Month 26 visit.

#### 4. ANALYSIS POPULATIONS

Population	Definition / Criteria		Analyses Evaluated	
All Participants	All Participants		Study Population	
Screened	For disposition displays, except for the listing of			
	subjects who were rescreened, only the latest re-			
	screening data will be included. All screening data			
	will be summarized or listed for other displays.			
All Participants	All participants transitioning from the LATTE study	•	Study Population	
Enrolled	and signed the informed consent form (ICF).			
Safety Population	All participants who receive at least one dose of IP	•	Safety	
	on or after Day 1 visit.		·	
	Participants will be assessed according to actual			
	treatment received.			
Intent-to-Treat	All participants who receive at least one dose of IP	•	Study Population	
Exposed	during on or after Day 1 visit.	•	Efficacy	
Population (ITT-	Participants will be analyzed according to the		,	
E)	selected treatment regardless of what treatment was			
	actually received. This population will be used for all			
	summaries unless otherwise specified.			

Population	Definition / Criteria	Analyses Evaluated
Per-Protocol Exposed (PP-E)	All participants in the ITT-E Population who comply with the protocol except for major protocol violators. Protocol deviations that would exclude subjects from the PP-E population are defined in Section 4.1 (Protocol Deviations) and Appendix 1 (Protocol Deviation Management and Definition for Per-Protocol Population).	• PP
Confirmed Virologic Failure (CVF)	All participants in the ITT-E population who met Confirmed Virologic Failure (CVF) criteria.	

Virology

Efficacy

Long-tem Follow- up	All subjects receiving at least one dose of CAB LA and/or RPV LA who have discontinued the CAB LA + RPV LA regimen and have at least one Long-term Follow-up phase clinic visit (i.e. have at least one long-term follow-up visit shown in the study database, LTFU month 1, LTFU month 3, etc).	Safety

Refer to Appendix 12: List of Data Displays which details the population used for each display.

#### 4.1. Protocol Deviations

Important protocol deviations (including deviations related to study inclusion/exclusion criteria, conduct of the trial, patient management or patient assessment) will be summarised and listed.

Important deviations which result in exclusion from the analysis population will also be summarised and listed. (Please refer to Appendix 1: Protocol Deviation Management and Definitions for Per Protocol Population).

Protocol deviations will be tracked by the study team throughout the conduct of the study in accordance with the Protocol Deviation Management Plan.

- Data will be reviewed prior to freezing the database to ensure all important deviations and deviations which may lead to exclusion from the analysis are captured and categorised on the protocol deviations dataset.
- This dataset will be the basis for the summaries and listings of protocol deviations.

A separate summary and listing of all inclusion/exclusion criteria deviations will also be provided. This summary will be based on data as recorded on the inclusion/exclusion page of the eCRF.

# 5. CONSIDERATIONS FOR DATA ANALYSES AND DATA HANDLING CONVENTIONS

## 5.1. Study Treatment & Sub-group Display Descriptors

Treatment Group Descriptions					
	RandAll NG Data Displays for Reporting				
Code	Description	Description	Order in TLF		
Α	CAB LA (600 mg) + RPV LA (900 mg) Q2M	Q2M	1		
В	Oral DTG (50mg) + RPV (25mg) daily	DTG + RPV	2		

#### 5.2. Baseline Definitions

Baseline information to be collected at Day 1 includes general medical history and current medical conditions. Laboratory and health outcomes assessments will also be assessed. Questionnaire/surveys are recommended to be administered at the beginning of the visit before any other assessments are conducted, in the order specified. For participants who agree to the optional assessment, a whole blood sample for genetic research should be collected at Day 1 (if not already collected during participation in the LATTE study). For all endpoints (except as noted in baseline definitions) the baseline value will be the latest pre-dose assessment with a non-missing value, including those from unscheduled visits. If time is not collected, Day 1 assessments are assumed to be taken prior to first dose and used as baseline. See the protocol Section 8.2 for more details.

Unless otherwise stated, if baseline data is missing no derivation will be performed and baseline will be set to missing.

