- a. The Day 1 visit will take place during Week 312 (or Week 324 in the event of unavoidable delays) of the LATTE study, the participant's last week on study. LATTE participants eligible for POLAR study dosing will take final dose of CAB 30 mg + RPV 25 mg in the clinic within 2 hours of the Q2M IM regimen. For IM dosing administration loading doses are required. (Day 1=1st loading dose; Month 2=2nd loading dose)
- b. Continue this pattern for visits for the remainder of the study. For example, Month 28 will be conducted just like Month 20, Month 30 will be conducted just like Month 22 and so on.
- c. Physical exams should be conducted as part of normal routine clinical care but data will not be collected in the electronic case report form (eCRF). Medical assessments include any decisions the study staff must make for participant management.
- d. Measure vital signs after about 5 minutes of rest in a semi-supine position.
- e. Height collected at Day 1 only.
- f. On Day 1, ECGs should be performed in triplicate at least 5 minutes apart and following 5 minutes of rest in a semi-supine position within 1 hour prior to first dose. Also on Day 1, a 2-hour post dose ECG will be performed for all participants. The 2-hour post dose ECG on Day 1 can also be used for the LATTE Week 312 (or Week 324, if needed) visit. ECG evaluations at other visits should be obtained after dosing, preferably 2-4 hours post dosing.
- g. A (-) urine pregnancy test is required prior to any injection and as required by medical monitor after a treatment interruption. A (+) urine test should be confirmed with a stat serum test. If (+), participant will need to be withdrawn.
- h. Plasma for storage samples are collected for possible future analyses, back-up in cases of loss/damage in transit and geno/pheno analyses for virologic failures.
- i. Fast overnight; however, a minimum of a 6 hour fast is acceptable.
- j. Take PK samples pre-dose.

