7.1.2. QTc Stopping Criteria

A participant who has a QTc interval >550 msec considered causally related to IP will be withdrawn from the study. The QTc should be based on averaged QTc values of triplicate electrocardiograms obtained over a brief (e.g., 5 to 10 minute) recording period.

If an alternative cause of the QT prolongation is determined (e.g., participant receiving drug known to cause prolonged QT or TdP), the IP may be restarted (or continued) after consultation and agreement with the Medical Monitor. RPV and RPV LA should not be administered to participants who are receiving a drug known to be associated with TdP.

When performing ECGs, the *same* QT correction formula *must* be used for *each individual participant* to determine eligibility for, and discontinuation from, the study. This formula may not be changed or substituted once the participant has been enrolled.

For example, if a participant is eligible for the protocol based on QTcB, then QTcB must be used for discontinuation of this individual participant as well.

Once the QT correction formula has been chosen for a participant's eligibility, the *same formula* must continue to be used for that participant *for all QTc data being collected for data analysis*. Safety ECGs and other non-protocol specified ECGs are an exception.

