## 12.3.2. Definitions of Assessment Windows for Data Other than Health Outcomes

Table 6 Assessment Windows for Screening and Maintenance Phase Data for CAB LA + RPV LA arm

All Parameters (except for where noted)	Target Study Day	Analysis Window	Analysis Timepoint
	1	Baseline information to be collected at nominal visit Day 1 which is the last available recorded value up to and including the Maintenance treatment start	Baseline

All Parameters (except for where noted)	Target Study Day	Analysis Window	Analysis Timepoint
		date, excluding 2-hour post-dose ECG taken on the Maintenance treatment start date	
	1	Date of first maintenance dose of IP+	Day 1
	31	2 ≤ Study Day ≤ 60	Month 2*
	91	61 ≤ Study Day ≤ 120	Month 4
	151	121 ≤ Study Day ≤ 180	Month 6
	211	181 ≤ Study Day ≤ 240	Month 8
	271	241 ≤ Study Day ≤ 300	Month 10
	331	301 ≤ Study Day ≤ 360	Month 12
	391	361 ≤ Study Day ≤ 420	Month 14
	451	421 ≤ Study Day ≤ 480	Month 16
	511	481 ≤ Study Day ≤ 540	Month 18
	571	541 ≤ Study Day ≤ 600	Month 20
	631	601 ≤ Study Day ≤ 660	Month 22
	691	661 ≤ Study Day ≤ 720	Month 24
	751	721 ≤ Study Day ≤ 780	Month 26
	(( m -1)*30)+1	$(((m-1)*30)-29) \le \text{Study Day} \le (((m-1)*30)+30)$	Month m , m =28, 30,
If a	If a participant permanently discontinued study treatment:		
NOTES		Date > max (Date of Last Oral Dose of CAB+RPV + 1, Date of Last Injection + 67)	Follow-up#

Table 7 Assessment Windows for Screening and Maintenance Phase Data for DTG + RPV arm

All Parameters (except for where noted)	Target Study Day	Analysis Window	Analysis Timepoint
	1	Baseline information to be collected at nominal visit Day 1 which is the last available recorded value upto and including the Maintenance treatment start date, excluding 2-hour post-dose	Baseline

+ Only non-baseline records from the mentioned assessment window will be assigned to Day 1.

\* The second loading injections will be administered 1 month (Month 2 visit, start of the second month of the study) after initial loading dose (CAB LA 600 mg + RPV LA 900 mg), with subsequent injections (CAB LA 600 mg + RPV LA 900 mg) occurring every 2 months thereafter.

# Follow-up will be derived only for participants who permanently discontinued study treatment.

All Parameters (except for where noted)	Target Study Day	Analysis Window	Analysis Timepoint
		ECG taken on the Maintenance treatment start date	
	1	Date of first maintenance dose of IP+	Day 1

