#### For data other than health outcome

- 1. The assessment closest to the window target Study Day;
- 2. If there are multiple assessments equidistant from the target Study Day, then the mean of these values will be used. For HIV-1 RNA, the geometric mean of the number of copies will be used as opposed to the arithmetic mean.

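### The SAP does not say whether baseline QTc is the last of the three Day 1 pre-dose tracings or their mean

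*SAP*

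**What the plan says.** **Collection.** Protocol 1.3 (and again 8.1 and 8.4.5) asks both arms for replicate tracings before the first dose: "On Day 1, ECGs should be performed in triplicate at least 5 minutes apart and following 5 minutes of rest in a semi-supine position". A further ECG follows 2 hours after dosing. After Day 1, ECGs are scheduled only at Month 12 and withdrawal, with no mention of replicates: "ECG evaluations at other visits should be obtained after dosing, preferably 2-4 hours post dosing".

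**Baseline rule.** SAP 5.2 states that, for all endpoints unless an exception is noted, "the baseline value will be the latest pre-dose assessment with a non-missing value, including those from unscheduled visits". No ECG exception is noted. It adds: "If time is not collected, Day 1 assessments are assumed to be taken prior to first dose and used as baseline". SAP 12.6.1 sends change from baseline back to 5.2. The Baseline rows of SAP Tables 6 and 7 define baseline as "the last available recorded value up to and including the Maintenance treatment start" date. They mention ECG only to exclude the 2-hour post-dose tracing.

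**Rule for several values in one window.** SAP 12.3.5 takes the value nearest the target day. If several are equally near, "then the mean of these values will be used". SAP 12.6.1 repeats the reference to 12.3.5 for multiple measurements at one time point.

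**Use.** SAP 8.4 and 12.8.2 flag a QTc above 500 msec or a rise from baseline of at least 60 msec. Table 3.16 summarises QTc change by category, and Listing 21 lists ECG values for participants with a flagged value.

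**The concern.** Three pre-dose tracings give a steadier estimate of a participant's starting QTc than one. A rule that keeps only the latest would give up that gain without any saving, and the noise would pass into every QTc change computed from it. With no true drug effect, a noisier change produces more apparent large rises and falls.

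The text also leaves gaps around the triplicate:

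- If tracing times are not recorded, 5.2 treats all Day 1 values as pre-dose but gives no order in which to pick the latest.
- A footnote to SAP Tables 6 and 7 sends only non-baseline records dated on the day of first dose to a Day 1 timepoint. If one tracing becomes the baseline, the other two could land there beside the 2-hour post-dose ECG and be averaged with it. The Screening-phase assignment in SAP Table 13 may prevent this, but the SAP does not say so.

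**Working it through.** The plan gives no figure for QTc precision, so there is nothing of its own to reproduce.

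**Step 1: which rule applies to the triplicate?**

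- *Latest tracing.* 5.2 and the Baseline rows both choose one last value. 12.3.5 starts only if several values remain after window assignment, and it is worded for choosing the value used in summaries of observed data. If it averaged all values from one date at baseline, *latest* in 5.2 would have no effect within Day 1.
- *Mean of three.* SAP 12.3.1 assigns ECGs to windows by actual date. The Baseline row has target Study Day 1 and is bounded by date. Three pre-dose tracings on that date are equally near the target, so the tie rule would average them.

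No order of precedence is written, nor whether a triplicate counts as one assessment or three.

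**Step 2: how much noisier would a single tracing be?**

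Inputs:

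- Baseline tracings used: k = 1 or k = 3 (Protocol 1.3).
- Tracings at the later visit: one (assumed, since no replicates are stated).
- Within-participant SD of one QTc reading: s (not in the documents; assumed 10 to 20 msec).
- Share of that variance arising between tracings on one day: f (not in the documents; 0 to 1). The rest is day-to-day variation, which same-day replicates cannot reduce.

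Var(change) = s²[2(1 − f) + f(1 + 1/k)]

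For k = 1 this is 2s². For k = 3 it is s²(2 − 2f/3). The ratio of the SDs, single to mean of three, is 1/√(1 − f/3).

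| f | Variance reduction with the mean of three | SD single ÷ SD mean |
|---|---|---|
| 0 | 0% | 1.000 |
| 0.25 | 8.3% | 1.044 |
| 0.5 | 16.7% | 1.095 |
| 0.75 | 25.0% | 1.155 |
| 1 | 33.3% | 1.225 |

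**Step 3: false rises of at least 60 msec at one later visit, with no true change**

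P = 1 − Φ(60 / SD of change). For example, with s = 15 and a single tracing, the SD is 15 × √2 = 21.2 and 60/21.2 = 2.83, so P = 0.23%. With the mean of three and f = 1, the SD is 15 × √(4/3) = 17.3 and 60/17.3 = 3.46, so P = 0.03%.

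| Assumed s (msec) | Single | Mean, f = 0.25 | Mean, f = 0.5 | Mean, f = 1 |
|---|---|---|---|---|
| 10 | 0.001% | <0.001% | <0.001% | <0.001% |
| 15 | 0.23% | 0.16% | 0.10% | 0.03% |
| 20 | 1.7% | 1.3% | 1.0% | 0.5% |

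Per 100 participants with one later ECG, the largest differences are about 0.23 − 0.03 = 0.2 false flags at s = 15 and 1.7 − 0.5 = 1.2 at s = 20.

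**The case against.** The strongest reply is that the SAP already averages. Windows go by date, the three tracings are tied, and 12.3.5 takes the mean of ties. SAP 5.2 never says that one tracing is used, and where times are missing it speaks of Day 1 assessments in the plural. On that reading nothing is lost. This stands as a possible reading. It therefore rules out the stronger statement a reader might infer, that every QTc change discards two of three tracings. It does not settle the matter, because nothing in 12.3.5 clearly overrides *latest* in 5.2.

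A second reply is that the answer may lie outside these documents. SAP 8.4 relies on sponsor data standards for ECG, Table 3.16 borrows another study's shell, and mock shells are available only on request. The case report form might hold one averaged value instead of three. That is fair, and it is a further reason to call this an unresolved rule and not a proven loss of data.

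A third reply concerns the protocol's own averaging statement, "The QTc should be based on averaged QTc values of triplicate electrocardiograms". A reader might take it to require a mean baseline. It sits in Protocol 7.1.2, the QTc stopping rule, and does not define the analysis baseline. Nor is sharper change-from-baseline estimation given as the reason for the triplicate: the Protocol 2.3.1 risk table says the Day 1 ECG is there to find participants whose QT is already prolonged. Both limits are accepted. The case for the mean rests on precision alone.

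**Conclusion.** The concern holds as an ambiguity. SAP 5.2 and the Baseline rows point to the latest tracing, 12.3.5 can be read as giving the mean, and the SAP does not choose. If the mean is meant, the loss is zero. If the latest tracing is meant, the SD of QTc change is 0% to 22.5% higher than it need be. The upper end requires fully independent noise between tracings taken minutes apart, so it is a bound and not an expected value. The range assumes one tracing at the later visit; the false-flag rates also assume normal errors and SDs that the documents do not supply.

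The reach is limited to Table 3.16, the 60 msec flag and Listing 21, all descriptive, in a study with no hypothesis tests. A reader might also infer that the QT prolongation event of special interest would be inflated. The documents do not support that: SAP 12.10 identifies it from MedDRA preferred terms of reported adverse events, not from the derived QTc change. The primary endpoint is not involved. This is a free improvement, not a threat to the trial's conclusions.

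**What to change.** In SAP 5.2 and in the Baseline rows of SAP Tables 6 and 7, add: *For ECG intervals, baseline is the arithmetic mean of the available Day 1 pre-dose tracings; these tracings are not assigned to the post-baseline Day 1 timepoint.* Cross-refer to 12.3.5 so that the two rules agree, and use this baseline for Table 3.16, the 60 msec flag and Listing 21. If the database already holds one averaged Day 1 value, say so in the same place.

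The cost is one sentence repeated in the Baseline rows and a line of programming. No visit, tracing or data collection changes.
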